**Statistical Analysis Plan**  
CX-4945 for Community-Acquired Pneumonia

Version Changed	Before	After
2.0→3.0	
Exploratory Endpoints Endpoints
 
 
The percentage of subjects achieving normalized [REDACTED] levels on Day 7
 
 
This assessment will only be conducted in subjects whose [REDACTED] levels exceed the upper limit of normal (ULN) at Visit 2.
 
(Time Frame: Day 7)
 
[REDACTED] Change from baseline in [REDACTED]
 
(Time Frame: Day 1 to Day 7, 15, and 29)
	
Exploratory Endpoints Endpoints
 
 
The percentage of subjects achieving normalized [REDACTED] [REDACTED] levels on Day 7
 
 
This statistical analysis will only be conducted in subjects whose [REDACTED] levels exceed the upper limit of normal (ULN) at Visit 2.
 
(Time Frame: Day 7)
 
 
Change from baseline in [REDACTED]
 
 
(Time Frame: Day 1 to Day 7, 15, and 29)
 
Note: If the flow cytometry analyses for [REDACTED] are not performed at the local site lab, the related endpoint can be omitted.

2.0→3.0	
Per-Protocol (PP) Population
 
The PP population is defined as the set of subjects who meet the ITT population and below requirements:
 
 
Receive at least 80% of 10 doses of investigational product during Days 1 – 6 or die before Day 6
 
Not associated with any major protocol violations that have impact on efficacy evaluation
 
 
This population will be identified before the database lock and will be used as the supportive analysis population for efficacy endpoints.
	
Per-Protocol (PP) Population
 
The PP population is defined as the set of subjects who meet the ITT population and below requirements:
 
 
Receive 80 – 120% of 10 doses of the IP during Days 1 – 6 or die before Day 6
 
Not associated with any major protocol violations that have impact on efficacy evaluation
 
 
This population will be identified before the database lock and will be used as the supportive analysis population for efficacy endpoints and AE.

2.0→3.0	
Modified Per-Protocol (PP) Population
 
The mPP population is defined as the set of subjects who meet the ITT population and below requirements:
 
 
Receive at least 80% of 10 doses of investigational product during Days 1 – 6 or die before Day 6
 
Complete the required visits by Visit 4 or die before Visit 4
 
Not associated with any major protocol violations that have impact on efficacy evaluation by Visit 4
 
 
This population will be identified before the database lock and will be used as the supportive analysis population for efficacy endpoints.
	
Modified Per-Protocol (PP) Population
 
The mPP population is defined as the set of subjects who meet the ITT population and below requirements:
 
 
Receive 80 – 120% of 10 doses of the IP during Days 1 – 6 or die before Day 6
 
Complete the required visits by Visit 4 or die before Visit 4
 
Not associated with any major protocol violations that have impact on efficacy evaluation by Visit 4
 
 
This population will be identified before the database lock and will be used as the supportive analysis population for efficacy endpoints.

### **3 STATISTICAL CONSIDERATIONS**

#### **3.1 ANALYSIS POPULATION**

The following populations will be introduced for statistical analysis.

Analysis population	Description
Intent-to-Treat (ITT) Population	All randomized subjects who receive at least one dose of CX-4945 or placebo
Per-Protocol (PP) Population	

• The set of subjects who meet the ITT population

• Receive 80 - 120% of 10 doses of the IP during Days 1 - 6 or die before Day 6

• Not associated with any major protocol violations that have impact on efficacy evaluation

Modified Per-Protocol (mPP) Population =Evaluable subjects	

• The set of subjects who meet the ITT population

• Receive 80 - 120% of 10 doses of the IP during Days 1 - 6 or die before Day 6

• Complete the required visits by Visit 4 or die before Visit 4

• Not associated with any major protocol violations that have impact on efficacy evaluation by Visit 4

ITT population will be used as the primary analysis population for efficacy endpoints and the analysis population for baseline data, safety and exploratory endpoints. PP population will also be applied on AE analysis. PP and mPP populations will be used as the supportive analysis population for efficacy endpoints.

All analyses will be performed on actual treatment taken unless otherwise specified. For PP and mPP populations, all inclusion and exclusion criteria should be fulfilled as applied in the latest version.

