3.4. Discontinuation of Study Intervention

Discontinuation of study product CX-4945/placebo does not mean discontinuation from the study, and the remaining study procedures will be completed as designated by this protocol. If a clinically significant finding is identified following the initiation of study treatment, the Investigator (or designee) will determine if any change in subject management is necessary. However, a subject should be discontinued from study product CX-4945/placebo in any of the following circumstances:

- A suspected Grade 3 or higher treatment-related AE (according to Common Terminology Criteria for Adverse Events (CTCAE) version 5.0)
- Any treatment-related SAE
- A subject receives baricitinib
- A subject receives warfarin
- The subject is pregnant

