7.2.2. Per-Protocol (PP) Population

The PP population is defined as the set of subjects who meet the ITT population and below requirements:

- Receive 80 – 120% of 10 doses of the IP during Days 1 – 6 or die before Day 6
- Not associated with any major protocol violations that have impact on efficacy evaluation

This population will be identified before the database lock and will be used as the supportive analysis population for efficacy endpoints and AE.

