**3.2.5 SAFETY ANALYSES**

**Treatment-emergent Adverse Events (TEAEs)**

**Statistical Analysis Plan**  
CX-4945 for Community-Acquired Pneumonia

---

AEs occurring during the study will be coded using the most recent version of Medical Dictionary for Regulatory Activities (MedDRA). The adverse events will then be grouped by MedDRA preferred terms into frequency tables according to system organ class. All reported adverse events, as well as adverse events judged by the investigator as at least possibly related to IP, will be summarized according to system organ class and preferred term within system organ class. When an adverse event occurs more than once for a subject, the maximal severity to the IP will be counted.

An overview of TEAEs will be presented with number and percentage. Separate summaries will be produced for the following categories, such as TEAEs, SAEs, Treatment-Related TEAEs, TEAEs resulting in discontinuation of study treatment and TEAEs leading to death will be presented. All coding terms will be included in the subject data listing.

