### **3.3.3 HANDLING OF PROTOCOL DEVIATIONS**

Protocol deviations, including operational and non-operational deviations, will be verified and logged according to SOP. Major DVs of this study, including the items below but not limited to, will be justified by the BSS upon the confirmation of sponsor. Relevant statistics are displayed in Tables 14.1.3.

- Violation of inclusion/exclusion criteria (wrong subject entry)
- Administration of prohibited therapy (medication / procedure / surgery)
- Non-compliant with the key study procedures
- Measurement/visit out of scheduled time window that may have significant impact on key efficacy / safety data
- Low treatment compliance / exposure
- Study was not withdrawn according to study withdrawal criteria

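### The supportive per-protocol AE tables leave out survivors who stop study drug for toxicity before the eighth dose, so their discontinuation row is truncated and other rates may look more favourable

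*SAP*

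**What the plan says.** SAP 3.1 defines ITT as everyone randomized who took at least one dose and makes it the "analysis population for baseline data, safety and exploratory endpoints". It then adds a second AE population: "PP population will also be applied on AE analysis". Protocol 7.2.2 agrees, saying that PP "will be used as the supportive analysis population for efficacy endpoints and AE". The protocol synopsis ticks PP beside ITT under the safety population and describes the PP use for adverse events as supportive. SAP 3.1 uses that label for PP only in connection with efficacy.

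Membership of PP depends on exposure ("Receive 80 - 120% of 10 doses of the IP during Days 1 - 6 or die before Day 6") and on protocol adherence ("Not associated with any major protocol violations that have impact on efficacy evaluation"). SAP 3.1 also requires PP subjects to meet the eligibility criteria of the latest protocol version. SAP 3.3.3 lists "Low treatment compliance / exposure" among the major deviations, without a numerical threshold.

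Protocol 3.4 calls for study product to stop in several circumstances. Two concern toxicity: "A suspected Grade 3 or higher treatment-related AE" and a treatment-related SAE. The same section keeps these subjects in the study with their remaining procedures. Protocol 3.5 adds that investigators may stop the drug for severe untoward effects, and that AEs are not grounds for ending study participation.

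SAP 3.2.5 lists the AE summaries, including "TEAEs resulting in discontinuation of study treatment and TEAEs leading to death will be presented".

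**The concern.** An AE table is meant to show what happened to those who were exposed. PP selects on the number of doses taken, which is a post-randomization variable that toxicity can cut short. The selection is therefore tied to the outcome being tabulated. Nothing in the PP definition serves a safety question, since its other criterion concerns violations that affect efficacy.

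The report would carry two sets of AE tables. The PP set may show fewer discontinuations and fewer severe related events in whichever arm had more early toxicity stops, and it could be cited for tolerability. The SAP gives no reason for producing it and no caution on how to read it.

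**Working it through.** The plan states no figure on this point, so there is nothing to reproduce. The check is of the rules against each other, followed by illustrative arithmetic.

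**Step 1, the dose threshold (SAP 3.1).** 0.80 × 10 = 8 doses and 1.20 × 10 = 12 doses. Seven doses is 70% and fails; eight is 80% and passes.

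**Step 2, the stopping rules (Protocol 3.4 and 3.5) against the PP rule.**
- Stops for toxicity after 1 to 7 doses and survives to Day 6: in ITT, not in PP.
- Stops for toxicity after 8 or 9 doses: in ITT, and can be in PP.
- Dies before Day 6: in ITT, and can be in PP whatever the dose count.

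Related Grade 3 or higher AEs and related SAEs face this selection when they lead to a stop before the eighth dose. Events that begin later do not cause removal by this route.

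**Step 3, the row for AEs leading to discontinuation.** Let n be the dosed subjects in an arm, k those who stop because of an AE, and r those of the k who remain in PP. If there are no other removals, ITT = k/n and PP = r/(n − (k − r)). SAP 3.4.1 gives 44 randomized. I assume 22 dosed per arm; k and r are also assumptions.

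| k | r | ITT | PP |
|---|---|---|---|
| 0 | 0 | 0/22 = 0% | 0/22 = 0% |
| 1 | 0 | 1/22 = 4.5% | 0/21 = 0% |
| 2 | 0 | 2/22 = 9.1% | 0/20 = 0% |
| 3 | 0 | 3/22 = 13.6% | 0/19 = 0% |
| 3 | 1 | 3/22 = 13.6% | 1/20 = 5.0% |
| 3 | 3 | 3/22 = 13.6% | 3/22 = 13.6% |

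The truncation follows from the rules alone. Its numerical effect depends on k and r.

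**Step 4, any other AE rate.** With x AE subjects among n, a of them removed and b AE-free subjects removed, ITT = x/n and PP = (x − a)/(n − a − b). PP is below ITT if and only if a/(a + b) > x/n. Take x = 11 of 22, a 50% rate. It is borrowed for scale only from the 5 subjects with drug-related diarrhoea in the Phase I 400 mg BID cohort (Protocol 1.2.1), which is 10 subjects if 30 were split 1:1:1.

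| a | b | ITT | PP |
|---|---|---|---|
| 1 | 0 | 50.0% | 10/21 = 47.6% |
| 2 | 0 | 50.0% | 9/20 = 45.0% |
| 3 | 0 | 50.0% | 8/19 = 42.1% |
| 1 | 1 | 50.0% | 10/20 = 50.0% |
| 1 | 2 | 50.0% | 10/19 = 52.6% |

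If early AE stoppers are the only removals, the rate falls. If enough AE-free subjects are also removed, it can stay level or rise.

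**Step 5, the arm contrast (assumed counts).** ITT: 11/22 − 6/22 = 50.0% − 27.3% = 22.7 points. If three AE stoppers leave the active arm and nobody leaves placebo: 8/19 − 6/22 = 42.1% − 27.3% = 14.8 points.

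**The case against.** The strongest reply is that no toxicity is lost from the report. ITT is the main safety population and contains every dosed subject. Early stoppers stay in follow-up and individual data are listed. Exposure and major deviations are summarized as well. The protocol calls the PP use supportive. All of this stands and limits the point to an additional set of tables.

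A second reply concerns the size. Protocol 1.2.1 says that every drug-related event in the Phase I study was mild, and that no treatment-related event reached Grade 3 in the earlier COVID-19 study at 1000 mg BID for 14 days. Those data do not show that either toxicity trigger in Protocol 3.4 was met, and nothing in the documents supports a particular number of early stops. This also stands: the counts above are assumptions, not forecasts.

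A reader might go further and infer that PP removes everyone who stopped because of an AE, or that it understates toxicity by construction. The documents support neither. Stops after 8 or 9 doses and deaths before Day 6 can remain in PP. PP can also lose AE-free subjects through low compliance, doses above 120%, major violations or the latest-version eligibility rule, and Step 4 shows that the rate can then rise. Only the discontinuation row is truncated by rule.

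The reply does not supply a purpose for the table. If it agrees with ITT it adds nothing. If it differs, the difference comes from who was removed.

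**Conclusion.** The concern holds in a limited form. Survivors who stop for toxicity after 1 to 7 doses are outside the PP AE tables by rule, so the PP discontinuation row cannot describe tolerability. Related Grade 3 or higher AEs and related SAEs are open to the same selection. For other AE rates a more favourable picture is expected, not certain.

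The size cannot be derived, because the documents give no count of early AE stoppers or of PP subjects per arm; with no early stoppers the effect is zero. The illustrations assume 22 dosed per arm and invented event counts. The main safety analysis is unaffected. This is a flaw in a supportive output of a small, early-terminated exploratory study, worth correcting because the correction is cheap.

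**What to change.** Delete the AE use of PP from SAP 3.1 and record it under SAP 3.4 as a change from Protocol 7.2.2 and the synopsis. The last subject has already left the study (SAP 2.5), so the SAP is the practical place for the change. Report AEs in all dosed subjects. If an exposure view is wanted, tabulate AEs in that same set by number of doses taken.

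If the PP AE tables are kept:
- label them supportive in the SAP;
- state that they will not be used for tolerability conclusions;
- omit the discontinuation row;
- show beside them, by arm, the number of dosed subjects excluded from PP and their AEs.

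The cost is some SAP wording and the loss of one supportive set of tables that protocol version 3.0 added. No data are lost, since every AE remains in the ITT tables and the listings.

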3.6. Method of Assigning Subjects to Treatment Groups

The study treatment will be randomly assigned to subjects. The randomized sequence of study treatments will be generated by a qualified biostatistician. The randomization schedule will be kept and maintained by the designated personnel before the study begins and until the database lock. The biostatistician prepares the schedule with a 1:1 randomization ratio (CX-4945: Placebo) by stratified randomization with study domains and study sites strata. Also, block permutation is used for generating randomization schedule. Eligible subjects will receive a random number at randomization. The subject will receive the corresponding treatment assigned by the EDC system. For any reason that a subject withdraws from the study prematurely after the randomization, his/her randomization number will not be reused. The next eligible subject will receive the lowest available randomization number.

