7.2. Datasets Analyzed

7.2.1. Intent-to-Treat (ITT) Population

The ITT population is defined as all randomized subjects who receive at least one dose of CX-4945 or placebo. This population will be used as the primary analysis population for efficacy endpoints and the analysis population for baseline data, safety and exploratory endpoints.

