### **3.3.7 USE OF AN “EFFICACY SUBSET” OF SUBJECTS**

In addition to ITT population, efficacy data will be analyzed in PP and mPP population.

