### **3.3.11 BY SUBJECT DISPLAY**

Individual subject data will be listed by measure and time point.

By-subject data are displayed in **Appendix 16.2**.

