#### **3.4.2 HANDLING OF DOMAIN IN STATISTICAL ANALYSIS**

For subjects with positive FilmArray results for both SARS-CoV-2 and Influenza Virus, the domain used for statistical analyses, including but not limited to subgroup analysis and ANOVA/ANCOVA modeling, will be conducted based on their randomized domain group.

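### SAP 3.1 groups every analysis by treatment actually taken and makes no exception for the primary ITT efficacy comparison, so that comparison is not by randomized arm if any subject took the other arm's product

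*SAP*

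**What the plan says.** SAP 3.1 gives the ITT set its role: "ITT population will be used as the primary analysis population for efficacy endpoints and the analysis population for baseline data, safety and exploratory endpoints". The paragraph that follows sets how subjects are grouped: "All analyses will be performed on actual treatment taken unless otherwise specified".

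The ITT definition fixes membership only. Protocol 7.2.1 reads "The ITT population is defined as all randomized subjects who receive at least one dose of CX-4945 or placebo", and SAP 3.1 has the same rule. Neither says in which arm a member is counted.

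The SAP has one as-randomized rule. For subjects positive for both viruses, SAP 3.4.2 says the domain used in analyses "will be conducted based on their randomized domain group". That settles domain, not treatment arm.

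On the other efficacy sets, SAP 3.3.7 says only that "In addition to ITT population, efficacy data will be analyzed in PP and mPP population".

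**The concern.** An ITT label tells the reader that subjects are compared in the arms to which they were randomized, because that is the comparison randomization protects. Grouping by product taken suits safety. In SAP 3.1, however, the rule covers all analyses, and ITT is the set used for efficacy, baseline, safety and exploratory work alike. A programmer who follows 3.1 literally would move a wrong-product subject out of the randomized arm and still title the table ITT.

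What is at stake is the meaning of the primary comparison, and its value only if such a subject exists. None is reported. Protocol 3.6 says "The subject will receive the corresponding treatment assigned by the EDC system", which makes a wrong product unlikely but does not exclude it.

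**Working it through.** **1. Does anything override the general rule?** The rule yields to a contrary specification, so each place that could contain one was read.

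| Place | What it says on arm grouping |
|---|---|
| Protocol 7.2.1; SAP 3.1 (ITT definition) | Membership only |
| SAP 3.2.2 | Summaries by study arm and tests between treatment groups; neither is defined as randomized or actual |
| SAP 3.2.3 | Fisher or CMH for the primary endpoint; no grouping rule |
| SAP 3.2.4 to 3.2.6 | Nothing |
| SAP 3.2.11, 3.3.2 | Nothing |
| SAP 3.3.7 | Names the PP and mPP sets; no grouping rule |
| SAP 3.4.1 to 3.4.5 | Randomized group for domain only (3.4.2) |
| Protocol, statistical methods | No as-treated rule and no as-randomized rule |

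No exception for treatment arm was found. The mock-up tables and listings specification (SAP 3.6) are separate documents that were not available.

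**2. How much could it matter?** The plan gives no figure to reproduce here. Inputs from the documents are 44 randomized (SAP 3.4.1) and 1:1 allocation (SAP 2.2). Assumptions not in the documents are a 22:22 split, exactly one wrong-product subject, 0 events on active, and e = 1, 3 or 5 events on placebo.

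Risk difference is active minus placebo, in percentage points. As randomized, it is 0/22 − e/22. As treated, there are three cases:

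- A: a placebo-randomized subject with an event took active: 1/23 − (e−1)/21
- B: a placebo-randomized subject without an event took active: 0/23 − e/21
- C: an active-randomized subject without an event took placebo: 0/21 − e/23

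| e | As randomized | A (shift) | B (shift) | C (shift) |
|---|---|---|---|---|
| 1 | −4.5 | +4.3 (8.9) | −4.8 (0.2) | −4.3 (0.2) |
| 3 | −13.6 | −5.2 (8.5) | −14.3 (0.6) | −13.0 (0.6) |
| 5 | −22.7 | −14.7 (8.0) | −23.8 (1.1) | −21.7 (1.0) |

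Shifts are computed before rounding. With e = 1, case A reverses the sign.

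**3. How likely is the large shift, given one wrong-product subject?** If each of the 44 is equally likely to be that subject, case A has probability e/44: 1/44 = 2.3%, 3/44 = 6.8%, 5/44 = 11.4%. The mean absolute shift is (e·A + (22−e)·B + 22·C)/44, which gives 0.40, 1.15 and 1.82 points for e = 1, 3 and 5.

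**4. Sensitivity to the zero-events-on-active assumption.** With 1 vs 3 or 2 vs 4 events (active vs placebo), non-event shifts are 0.8 to 1.3 points and event shifts 7.9 to 8.3. For 2 vs 4, the chance that the wrong-product subject had an event is 6/44 = 13.6%, and the mean absolute shift is about 2.1 points.

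**5. No wrong-product subject.** The two groupings coincide and the shift is 0.

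**The case against.** The best counter-argument is textual. Protocol 3.1 and 3.2.1 describe arms as what subjects are randomized into, and SAP 3.2.2 summarizes by study arm; on that reading, study arm already means randomized arm and the exception exists. This is an inference from an undefined term. SAP 3.2.2 also speaks of treatment groups, and the arms are named by product. It does not displace an express rule covering all analyses, though it suggests the drafters may not have intended as-treated efficacy.

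The sentence also has an evident purpose. The amendment table in SAP 2.5 shows that the separate safety population was dropped at protocol version 2.0, so ITT now serves safety too, where actual treatment is the natural grouping. That explains the sentence but does not limit it.

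Three further points stand and hold the weight of the finding down. The mock-up tables may group ITT efficacy correctly, so the finding is about the SAP text. A wrong-product subject could be found from the deviation tables ("Relevant statistics are displayed in Tables 14.1.3") or the listings ("Individual subject data will be listed by measure and time point"), so concealment is not alleged; detection alone would not change the estimate reported under the rule. And the last subject left on 22-APR-2025, before the SAP of 25-JUN-2025, so no new case can arise.

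It can also be said that the shift ranges depend on assumed event counts. They do: with events in both arms they widen slightly, as step 4 of the working shows.

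**Conclusion.** The concern holds on the SAP text, which as written does not give a by-randomized-arm primary comparison. Confidence is high about what 3.1 says; how the ITT efficacy tables are actually programmed cannot be seen from these documents.

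The consequence is conditional and modest. With one wrong-product subject, the shift in the primary risk difference would usually be about 1 point, and about 8 to 9 points only if that subject also had an event. These sizes rest on the assumed 22:22 split and event counts. No claim is made about statistical significance. The protocol states no primary hypothesis, and its sample size was not based on power. The point should be fixed because the label and the rule conflict and the correction is almost free, not because a result is known to be wrong.

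**What to change.** Keep the existing sentence in SAP 3.1 and add after it:

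> Exception: efficacy, baseline and exploratory analyses on the ITT population are by randomized arm; safety analyses, and PP and mPP analyses, are by treatment actually received.

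The minimum needed is the efficacy part. Baseline is included because it describes the arms that ITT efficacy compares, and exploratory because those endpoints are also compared between arms on ITT. If the mock-up tables already use the randomized arm, bring 3.1 into line with them.

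Report the number of subjects whose product taken differed from their randomized arm, including zero, in the major-deviation tables of SAP 3.3.3 or in the disposition summary. A reported zero shows that the two groupings agree.

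The cost is one sentence and one count in an existing table. The arm variable in the ITT efficacy, baseline and exploratory programs changes only if it is not already the randomized arm.
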